7.4.1 Participants Who Become Infected with HIV

Participants who test positive for HIV prior to randomization will not be eligible to continue participating in the study. If a participant tests positive for HIV after randomization, the participant will be referred to local care and treatment services and may return to the research clinic for additional counseling and other support services, as needed. Continued study participation would be of no added benefit and thus follow-up visits will be discontinued, study product use will cease, and the participant will be considered terminated from the study. Participants who become infected after randomization may be offered additional laboratory testing (such as HIV RNA and HIV drug resistance testing), as clinically indicated per discussions between IoR/designee and MATRIX. Please reference the MATRIX-001 SSP Manual for additional details (www.matrix4prevention.org).

7.4.2 Participants Who Become Pregnant

Participants must be protected from pregnancy as described in Section 5.2. A pregnancy test will be performed at clinic visits per Appendix I. A pregnancy test will be done at other visits, if indicated. If pregnancy is confirmed, the participant will be referred for follow-up and discontinued from use of study product (if initiated). Every effort will be made to follow the pregnancy to outcome.

Any pregnancy that occurs while a participant is taking study drug product must be recorded in the Antiretroviral Pregnancy Registry (APR) online at <http://www.apregistry.com/>. The Investigator must register the pregnancy within fifteen (15) calendar days of first becoming aware of the pregnancy and maintained through to pregnancy outcome. A copy of the report will be provided to the sponsor and reported to the IRB/IEC, as needed, in accordance with local requirements.

7.4.3 Participants Who Temporarily Hold or Permanently Discontinue Study Product Use

Participants with a temporary product hold due to an AE or STI where short-term resolution is possible will continue their scheduled follow-up visits and have all protocol-specified study procedures except the following:

- Provision of vaginal insert, product use instructions, and product use adherence counseling.

The above study procedures are to resume at follow-up visits once study product use is resumed.

Participants who permanently discontinue study product use for any clinician-initiated reason other than HIV infection or pregnancy will discontinue study follow-up visits and procedures, as continued study participation would be of no added benefit. Participants will, however, be asked to complete all the procedures scheduled to occur at the SEV (Visit 8), if willing.

Note: The MATRIX-001 Management Team, in consultation with CONRAD, may provide guidance to the site regarding a modified study visit schedule to ensure PK samples are collected at the appropriate time points and/or omitted if the collection of samples would not be anticipated to yield analyzable data. Participants' duration of use and timing of study product hold/permanent discontinuation will be factored into a modified schedule. Refer to the MATRIX-001 SSP Manual for additional details.

Participants who permanently discontinue study product use due to an AE must continue to be followed in the study, if they are willing, until resolution (return to baseline) or stabilization of the AE is documented.

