3.2 Secondary Objectives

Pharmacokinetics (PK)

- To characterize the multi-compartmental PK profile of the TAF/EVG insert administered vaginally in multiple doses

Modeled *in vitro* PD

- To characterize the anti-HIV activity of the TAF/EVG insert in CVF administered vaginally in multiple doses
- To characterize the anti-HSV activity of the TAF/EVG insert in CVF administered vaginally in multiple doses

Acceptability

- To explore user experiences and identify product attributes considered likely to challenge and/or facilitate future sustained use of the TAF/EVG insert applied vaginally

Subclinical Safety and Vaginal Microbiome

- To characterize changes from baseline in soluble and cellular CV mucosal markers after multiple dose vaginal administration of the TAF/EVG insert
- To characterize changes from baseline in the vaginal microbiota after multiple dose vaginal administration of the TAF/EVG insert

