7.7 Behavioral Evaluations

Participants will respond to interviewer-administered questionnaires at the Screening visit (Visit 1), Enrollment visit (Visit 2), and post-dose Visits 3, 4, and 7. The baseline assessments, done at Screening and Enrollment, will include, among other topics, demographics, questions on participants' prior experience and comfort using vaginal products as well as other vaginal hygiene

practices. Brief product use assessments between Enrollment and Visit 7 will explore reactions to study product and administration method. For example, we will ask about comfort with insertion, sensation with the product *in situ*, and acceptability of vaginal discharge. A follow-up behavioral, product use, and acceptability questionnaire will be administered at Visit 7 and will examine overall satisfaction with the product after using it, multiple components and correlates of acceptability, as well as relevant topics such as adherence and preference. The design of these assessments is informed by a recent systematic review of the Theoretical Framework of Acceptability (Sekhon),³² published by Ortblad et al.,³³ and review of acceptability assessments in clinical trials research. These assessments will allow us to identify product attributes likely to challenge and/or facilitate future sustained use when applied vaginally by participants. Suggestions for product improvement will also be collected.

An in-depth interview is planned at study exit (Visit 8) with a sub-set of approximately 24 participants (~8 per site). These will be conducted using a semi-structured guide with, among other topics, questions on user acceptability of the product, user-centered suggestions for product design, packaging and delivery, and experiences with the direct application method. These IDIs will be conducted by a trained qualitative interviewer and will follow a semi-structured questionnaire guide. They are anticipated to last approximately 45-60 minutes. The interview notes, recording and transcripts from the in-depth interview will be considered as source documentation. The IDIs may be conducted in-person or remotely over a secure digital platform.

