9.3 General Criteria for Temporary Hold and Permanent Discontinuation of Study Product

A participant will be permanently discontinued from product use by the IoR/designee for any of the following reasons:

- Failure to follow protocol requirements that is judged severe enough by the investigator to significantly affect study outcomes
- HIV acquisition
- Pregnancy or expresses a desire to become pregnant
- SAEs or other serious medical reasons, as judged by the IoR/designee

A participant will be temporarily held from product use by the IoR/designee for any of the following reasons:

- Grade 2 or higher AE/SAE where short-term resolution is possible
- STI acquisition where short-term resolution is possible

The IoR/designee must consult the PSRT on all temporary product holds instituted at their discretion for further guidance on resuming product use, continuing the temporary hold, or progressing to permanent discontinuation. If product use is temporarily held/permanently discontinued at IoR/designee discretion, but the underlying reason for the temporary hold later resolves, the IoR/designee should consult the PSRT to resume product use at that time. All AEs are defined by the DAIDS Table for Grading the Severity of Adult and Pediatric Adverse Events, as outlined in Section 8.3.

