9.6 Criteria for Early Termination of Study Participation

Participants may voluntarily withdraw from the study for any reason at any time. IoRs/designees also may withdraw participants from the study to protect their safety and/or if they are unwilling or unable to comply with required study procedures, after consultation with the PSRT. Participants also may be withdrawn if CONRAD, USAID, MATRIX, government or regulatory authorities, including the South African Health Products Regulatory Authority (SAHPRA), Kenya Pharmacy and Poisons Board (KPPB), FDA and Office for Human Research Protections (OHRP), or site IRBs/IECs terminate the study prior to its planned end date. Every reasonable effort is made to complete a final evaluation of participants who withdraw or are withdrawn from the study prior to completing follow-up (see details regarding the Early Termination Visit in Section 7.3.5). Study staff members will record the reason(s) for all withdrawals in participants' study records.

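### End-of-use satisfaction, preference and adherence ratings are collected only at Visit 7, and women who leave earlier are directed to an exit visit that has no questionnaire

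*Protocol*

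**What the plan says.** **Timing and content.** Section 7.7 states: "A follow-up behavioral, product use, and acceptability questionnaire will be administered at Visit 7". Besides satisfaction after use, this form covers "multiple components and correlates of acceptability, as well as relevant topics such as adherence and preference". After the Visit 1 and 2 baseline forms, questionnaires are given at "post-dose Visits 3, 4, and 7". The earlier ones are shorter: "Brief product use assessments between Enrollment and Visit 7 will explore reactions to study product and administration method". Their examples are ease at insertion, how the product feels in place and how discharge is tolerated. Tables 5 and 6 (Visits 5 and 6) contain no product use assessment, and Appendix I agrees.

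**Early leavers.** Section 7.4.3 ends follow-up visits after a permanent clinician-initiated stop for reasons other than HIV infection or pregnancy. It then says: "Participants will, however, be asked to complete all the procedures scheduled to occur at the SEV (Visit 8), if willing". For participants who withdraw or are withdrawn, Section 9.6 promises a final evaluation and adds "see details regarding the Early Termination Visit in Section 7.3.5". Section 7.3.5 describes only Visit 8, the study exit visit. The behavioral content of Table 8 is HIV counselling and an in-depth interview in a subset, put at about 24 women in Section 7.7.

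**Objective.** Section 3.2 wants to "identify product attributes considered likely to challenge and/or facilitate future sustained use".

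**The concern.** Women who stop early bear directly on an objective about what makes continued use hard. Some may leave because they dislike the product or cannot keep to the regimen. One ground for permanent discontinuation in Section 9.3 is "Failure to follow protocol requirements that is judged severe enough by the investigator to significantly affect study outcomes". If these women are never asked the end-of-use questions, the post-use summary describes only those who reached Visit 7. The planned comparison of ratings between first insertion and actual use (10.8.3) depends on the later rating, so it has the same gap. This is a matter of data collection fixed in the protocol: no analysis plan can recover answers that were never requested.

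**Working it through.** The plan gives no figure on this point, so there is none to reproduce. The check compares the schedule with the exit routes and then illustrates size.

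**Step 1: what a leaver has been asked, by time of exit** (Sections 6.1, 7.2.2, 7.3 and 7.7; Tables 3 to 8; Appendix I)

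| Leaves | Last structured product rating | Doses scheduled by then |
|---|---|---|
| After Visit 3, before Visit 4 | Brief, Visit 3 | 1 to 3 |
| After Visit 4, before Visit 5 | Brief, Visit 4 | 3 |
| From Visit 5, before Visit 7 | Brief, Visit 4 | 4 to 10 |
| Temporary hold only | Full, Visit 7 (scheduled visits continue, 7.4.3) | depends on the hold |

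Section 6.1 gives 10 doses: 3 daily and 7 on alternate days. A woman who stops during the alternate-day phase leaves no questionnaire rating of it.

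**Step 2: whether another route supplies the form.** Section 7.4.3 allows a modified visit schedule, but it is framed around PK samples. Women with HIV infection or pregnancy are terminated (7.4.1, 9.5). The Section 9.6 reference leads to Visit 8. No stated route gives an early leaver the Visit 7 form.

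**Step 3: whether the loss could be selective.** The grounds for stopping include non-compliance and serious medical reasons (9.3). Early leavers may be replaced to reach 60 complete participants (10.6). Missing answers stay missing and only observed values are analysed (10.8.4).

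**Step 4: size.** The protocol gives no expected rate of product discontinuation. The 95% retention target (5.1.2) implies 0.05 × 60 = 3 losses among 60 women. Assume true willingness of 48/60 = 80%. With m leavers, w of them willing, the observed share is (48 − w)/(60 − m).

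- m = 1, w = 0: 48/59 = 81.4%
- m = 2, w = 0: 48/58 = 82.8%
- m = 3, w = 0: 48/57 = 84.2%
- m = 3, w = 1: 47/57 = 82.5%
- m = 3, w = 2: 46/57 = 80.7%
- m = 3, w = 3: 45/57 = 78.9%

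The shift runs from about +4 points to −1 point, depending on who leaves.

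**Step 5: the same with replacement.** For 60 completers at 95% retention, 60/0.95 = 63.2, so 64 women are needed and about 4 lack the form. Assume 87.5% of completers are favourable. This borrows the baseline interest of 14 of 16 women in the single-dose study (2.5.5) and serves only as an illustration. Then 60 × 0.875 = 52.5. The share among all 64 is 52.5/64 = 82.0% if none of the 4 is favourable, and (52.5 + 2)/64 = 85.2% if half are. The completer figure is then too high by 5.5 or 2.3 points.

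**The case against.** A reader might infer that acceptability is rated only by women who reach the end of dosing. The documents do not support that. Every woman who attends Visits 3 and 4 gives a brief rating, and the endpoint in Section 10.2 covers responses at enrollment and after dosing, so those ratings count. Women on a temporary hold keep Visit 7. The Visit 8 interview covers acceptability and is not limited to completers. What remains missing is the end-of-use content and any questionnaire rating of the alternate-day phase.

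Section 10.6 also includes in the analysis everyone with baseline sampling. That keeps early leavers in the data set but does not create answers they were not asked for.

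The Section 7.4.3 sentence covers only clinician-initiated stops. A woman who leaves because she dislikes the product would more likely withdraw herself, under Section 9.6. That section names an early termination visit which Section 7.3.5 never defines separately, so its content is inferred: the only procedures found there are those of Visit 8.

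Non-compliance in Section 9.3 means protocol requirements in general, not specifically missed doses. Section 7.8 also has counsellors ask whether instructions were followed. Both points limit the claim about adherence to questionnaire-reported adherence.

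Nor can upward bias be stated as fact. Exits for HIV infection, pregnancy or a wish to conceive need not reflect dislike. Placing every loss in one arm gives larger shifts, such as 24/30 = 80% reported as 24/27 = 89%, but nothing in the protocol supports that allocation, and Section 10.8.3 specifies no acceptability comparison by arm.

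**Conclusion.** The point holds in a limited form. End-of-use satisfaction, preference and questionnaire-reported adherence are missing by design for women who exit before Visit 7. The post-use summary and the comparison over time may be too favourable as a result. The number affected is probably small, about 3 or 4 at the retention target. That target is not a product-stopping rate, and it also counts losses after Visit 7, so the true number could be lower or higher. Under the stated assumptions the overall shift is a few percentage points: 80% to 84% with 3 unwilling leavers among 60, and close to zero or slightly reversed if the leavers resemble the rest. This is a named secondary endpoint in a Phase 1 safety and PK study. The primary endpoint is untouched. The change is worth making because it is cheap and the answers cannot be obtained later.

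**What to change.** In Section 7.4.3, Section 7.3.5 with Table 8, and Appendix I, state that any participant who has used product and exits before Visit 7, by clinician decision or her own, is offered the existing Visit 7 behavioral, product use and acceptability questionnaire at her exit contact, by telephone if needed. Include these responses in the post-use summary, identified as early-exit. The Section 9.6 reference to Section 7.3.5 would then lead to defined content.

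No added item on the reason for stopping is needed: Section 9 already has permanent discontinuations documented on CRFs, and Section 9.6 has the reasons for withdrawal recorded. The choice of women for the interview subset can stay as it is.

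The cost is one line in each of two tables, a sentence or two of text, and a slightly longer exit contact for a few women. Some answers will come at a different time from the last dose, or by telephone, which is why they should be labelled. Women who cannot be reached or who decline will still be missing.

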7.5 Interim Visits/Contacts

Interim visits may be performed at the participant's request or as deemed necessary by the investigator at any time during the study. The participant will be instructed to contact the site at any time during the study if she experiences moderate to severe urogenital symptoms (e.g., genital burning, irritation, stinging, pressure, rash, itching, discharge, urgency, dysuria, or hematuria), or if she experiences pelvic/lower abdominal pain, or moderate to heavy menstrual bleeding (more than she would have during a normal period). The participant will be asked to come in for an evaluation, as indicated.

Interim visits or procedures (e.g., pregnancy test, physical and/or pelvic examination, blood laboratory assessments, urine dipstick, microscopy, culture, STI testing, wet prep, and/or pH) may be performed as deemed necessary by the investigator. The participant will be asked to come in for an evaluation, as indicated. Interim visits after baseline sampling that require examination or interview due to symptoms will be recorded on CRFs.

When an interim visit occurs in response to an AE experienced by a study participant, study staff will assess the reported event clinically and provide or refer the participant to appropriate medical care, as necessary. All AEs will be evaluated and follow-up of any observed abnormalities will proceed according to Section 8.3.

7.6 Final Contact

Since participants' SEV include laboratory testing for HIV, additional contacts after the Visit 8 SEV may be required to provide them additional study test results, and post-test counseling, if needed. In addition, for participants who become pregnant during study participation, additional contacts may be required to ascertain the participant's pregnancy and infant outcome (see Section 7.4.2 for details). Study sites may complete these contacts at the study clinic or at community-based locations, depending on site capacities and site and participant preferences. All final contacts will be documented in participant study records.

7.7 Behavioral Evaluations

Participants will respond to interviewer-administered questionnaires at the Screening visit (Visit 1), Enrollment visit (Visit 2), and post-dose Visits 3, 4, and 7. The baseline assessments, done at Screening and Enrollment, will include, among other topics, demographics, questions on participants' prior experience and comfort using vaginal products as well as other vaginal hygiene

practices. Brief product use assessments between Enrollment and Visit 7 will explore reactions to study product and administration method. For example, we will ask about comfort with insertion, sensation with the product *in situ*, and acceptability of vaginal discharge. A follow-up behavioral, product use, and acceptability questionnaire will be administered at Visit 7 and will examine overall satisfaction with the product after using it, multiple components and correlates of acceptability, as well as relevant topics such as adherence and preference. The design of these assessments is informed by a recent systematic review of the Theoretical Framework of Acceptability (Sekhon),³² published by Ortblad et al.,³³ and review of acceptability assessments in clinical trials research. These assessments will allow us to identify product attributes likely to challenge and/or facilitate future sustained use when applied vaginally by participants. Suggestions for product improvement will also be collected.

An in-depth interview is planned at study exit (Visit 8) with a sub-set of approximately 24 participants (~8 per site). These will be conducted using a semi-structured guide with, among other topics, questions on user acceptability of the product, user-centered suggestions for product design, packaging and delivery, and experiences with the direct application method. These IDIs will be conducted by a trained qualitative interviewer and will follow a semi-structured questionnaire guide. They are anticipated to last approximately 45-60 minutes. The interview notes, recording and transcripts from the in-depth interview will be considered as source documentation. The IDIs may be conducted in-person or remotely over a secure digital platform.

7.8 Protocol and Product Adherence Counseling

Contraception counseling will be provided to participants of childbearing potential at all visits beginning at the Screening Visit. Protocol adherence counseling will be provided at all visits beginning at the Screening Visit. Counseling will be provided by different site staff than those conducting the behavioral assessments in accordance with standard study methods and as specified in site SOPs.

Counseling also will include reminders regarding concomitant medication, sexual activity, intravaginal product use and practices, and behavioral restrictions during study participation. The participant will be asked to abstain from any vaginal and anal activity, douching, and use of all intravaginal objects and products at specified times (see Section 6.7.2). The participant will be asked if she followed the relevant study instructions and if she did not, will be reminded of protocol requirements and the visits may be rescheduled.

7.9 Clinical Evaluations and Procedures

Physical Examination and Medical History

The full physical examination will include general appearance, height, weight, vital signs, and evaluation of body systems as outlined in the MATRIX-001 SSP Manual. Participants will be asked about medications/therapies at every visit, including Visit 1. Vital signs and weight will be taken at all visits after Screening (after Visit 1). Study staff will ask about adverse events at all visits after baseline sampling (after visit 2). A full physical examination will be completed by the clinician at Screening. Thereafter, a directed physical examination will be performed to assess any complaints or symptoms as clinically indicated.

Pelvic Examination

Pelvic exams will be performed using visual inspection of external genitalia and using a speculum for examination of the cervix and vagina. Bimanual exam may be performed as needed (required at Screening Visit). Pelvic exams will be conducted at each visit for PK, PD and subclinical safety specimen collection and as indicated based on participant reports. CVF will be collected using swabs. Further specimen collection procedures will be detailed in the SSP. Biopsy areas will be checked for healing at applicable visits and as indicated.

Rectal Fluid Collection

For participants who consent to RF collection, this sample will be collected using a swab at certain visits to assess drug concentrations.

Cervicovaginal Tissue Collection

CVT will be obtained at Visits 2, 4 and 7 (per sampling timepoint randomization) to assess pharmacokinetics, pharmacodynamics, and anti-HIV activity.

The study site should carefully record the date and time of each collection of blood, CVF, and CVT biopsies. The time of sampling will be based on the time the first sample is taken (when multiple sample types are being collected at a time point, all samples should be collected within a short period). Samples collected outside the sampling windows below will be considered a protocol deviation:

- ± 4 hours outside of the 24 hour time point
- ± 8 hours outside of the 48 and 72 hour time points
- + 4 days outside of the 10 days time point

Note: Detailed information regarding the rectal and genital examination, as well as the associated procedures required for collecting specimens at each visit, can be found in the MATRIX-001 SSP Manual.

Additional clinical assessments/procedures may be performed at the discretion of the examining clinician in response to symptoms or illnesses present at the time of the exam/procedure.

